17.4. LABORATORY EVALUATIONS

Laboratory evaluations will be performed in the site laboratory. Laboratory evaluations to be included in the outputs are included in the protocol, section 5.7.10, including hematology, chemistry panel, serum amylase and lipase, fasting lipid profile, coagulation, thyroid hormones, serum β -2 microglobulin, viral serology, urinalysis, leukocyte immunophenotyping, pregnancy testing, serum immunoglobulins assessment from the study site's local laboratory. All laboratory results (including pregnancy test results) will be included in listings.

Laboratory results will be converted to International Standard Units (SI Units), and all the analysis and presentation will be based on SI units.

The incidence of patients with the following elevations abnormal liver function tests (Hy's Law) at post-baseline will also be summarized:

- ALT or AST >3 x ULN and <= 5 x ULN (based on the worst post-baseline case)
- ALT or AST > 5 x ULN (based on the worst post-baseline case)
- Total bilirubin >= 2 x ULN (based on the worst post-baseline case)
- (ALT or AST >3 x ULN) and total bilirubin >= 2 x ULN [defined as total bilirubin increase by >= 2 x ULN within 14 days after ALT or AST increase by > 3 x ULN]
- Hy's law: (AST or ALT >3 x ULN) and total bilirubin >= 2 x ULN and ALP < 2 x ULN [defined as total bilirubin increase by >= 2 x ULN and ALP increase <2 x ULN within 14 days after ALT or AST increase by > 3 x ULN]

All laboratory evaluation records and abnormal liver function will be listed.

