5.1.2 Exclusion Criteria

Patients who meet any of the following criteria will be excluded from study entry:

1. Patients with primary central nervous system (CNS) lymphoma;
2. Any of the following laboratory abnormalities:
 - Absolute neutrophil count $<1.0 \times 10^9/L$
 - Hemoglobin $< 80 \text{ g/L}$
 - Platelets $<50 \times 10^9/L$

NOTE: In the dose expansion stage, patients with cell counts below the thresholds listed above may be considered eligible if, in the investigator's opinion, the reason is bone marrow infiltration. The investigator will discuss the eligibility of such patients with the sponsor, and only upon approval by the sponsor will a patient with cell counts below the thresholds be enrolled in the study.

NOTE: In the dose expansion stage, patients with \leq Grade 2 neutropenia per CTCAE version 5.0 and/or thrombocytopenia and with confirmed bone marrow infiltration are eligible.

3. Inadequate organ function, defined by the following:
 - Total bilirubin >1.5 times the upper limit of normal (\times ULN), with the following exception:
 - Patients with known Gilbert's disease who have serum total and direct bilirubin level $\leq 2.5 \times$ ULN and normal AST and ALT can be enrolled.

- AST or ALT $> 2.5 \times$ ULN, with the following exception:
 - In the dose expansion stage, patients with documented disease infiltration of the liver may have AST and ALT levels $\leq 5 \times$ ULN.
 - Estimated creatinine clearance (CrCl) per Cockcroft-Gault
 - Dose escalation stage of trial (Stage 1) – CrCl < 40 mL/min
 - Dose expansion stage of trial (Stage 2) – CrCl < 30 mL/min
4. International normalized ratio (INR) $> 1.5 \times$ ULN, activated partial thromboplastin time (aPTT) $> 1.5 \times$ ULN;
- Patients requiring anticoagulation therapy but with a stable INR within the recommended range according to the local guideline are eligible.
- NOTE: Patients may be considered for this study if kidney function is impaired but this impairment is believed to be a result of the patient's underlying disease. The investigator will discuss the eligibility of such patients with the sponsor, and only upon approval by the sponsor will a patient with impaired kidney function due to underlying disease be enrolled in the study.
5. Serum amylase or lipase $> ULN$ at screening or known medical history of serum amylase or lipase $> ULN$;
- NOTE: Patients with known medical history of serum amylase or lipase $> ULN$ are eligible in the dose expansion stage.

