16. Treatment within a clinical study of an investigational agent or using an investigational device within 30 days prior to initiation of the current study treatment;
17. Adverse events from prior anti-neoplastic therapy that have not resolved to Grade \leq 1, except for alopecia;
18. Pregnant (positive urine or serum beta human chorionic gonadotropin [β -HCG] test) or lactating women;
19. New York Heart Association (NYHA) Class II or greater congestive heart failure;
20. Congenital long QT syndrome or corrected QT interval (QTc) $>$ 470 msec;
21. Currently use medication known to cause QT prolongation or torsades de pointes (see full list at [http:// www.crediblemeds.org](http://www.crediblemeds.org));
22. History of myocardial infarction or unstable angina within 6 months prior to initiation of study treatment;
23. History of stroke or transient ischemic attack within 6 months prior to initiation of study treatment;
24. Inability to take oral medication, prior surgical procedures affecting absorption, or active peptic ulcer disease;
25. History of inflammatory bowel disease (e.g., Crohn's disease or ulcerative colitis);
26. Patients with ongoing chronic gastrointestinal diseases;
27. Legally protected adults;
28. Any other diseases, metabolic dysfunction, physical examination finding, or clinical laboratory finding that, in the investigator's opinion, gives reasonable suspicion of a disease or condition that contraindicates the use of an investigational drug or that may affect the interpretation of the results or renders the patient at high risk of treatment complications.

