6.3.1.5 Abnormal Liver Function Test Results

The finding of an elevated ALT or AST in combination with either an elevated total bilirubin ($\geq 2\times$ ULN) or clinical jaundice in the absence of cholestasis or other causes of hyperbilirubinemia is considered to be an indicator of severe liver injury (as defined by Hy’s law). Briefly, Hy’s Law cases have the following three components:

1. The drug causes hepatocellular injury, generally shown by a higher incidence of 3-fold or greater elevations above the ULN of ALT or AST than the (non-hepatotoxic) control drug or placebo;
2. Among trial patients showing such AT elevations, often with ATs $>3\times$ ULN, one or more patients also show elevation of serum TBL to $>2\times$ ULN, without initial findings of cholestasis (elevated serum ALP);
3. No other reason can be found to explain the combination of increased AT and TBL, such as viral hepatitis A, B, or C; preexisting or acute liver disease; or another drug capable of causing the observed injury.

Therefore, investigators must report as an AE in the occurrence of either of the following:

- Treatment-emergent ALT or AST $\geq 3\times$ ULN in combination with total bilirubin $\geq 2\times$ ULN; or
- Treatment-emergent ALT or AST $\geq 3\times$ ULN, in combination with clinical jaundice.

The most appropriate diagnosis or (if a diagnosis cannot be established) the abnormal laboratory values should be recorded on the Adverse Event CRF (see Section 6.3.1.4) and reported to the sponsor’s designee as a non-serious AE of special interest (see Section 6.2.3).

The guidance on diagnosis and management of hepatic AEs (including Hy’s law) can be found in Section 6.8, Table 8.

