Grade 3 AST/ALT elevation (>5 to 20 times ULN or from baseline, if baseline is abnormal)	
 Evaluate differential diagnosis and causality (including pre-existing liver disease and infectious etiology) Close monitoring for any clinical symptoms Weekly monitoring of transaminase and bilirubin levels until return to Grade 1 or <3 times ULN Consider hepatic consult and treat accordingly per standard treatment guidelines Permanently discontinue study drug if the patient meets the definition of Hy's law 
 AST or ALT value > 3 × ULN and TBL > 2 × ULN No other reason to explain combination of increased AST or ALT and TBL, ALP normal (i.e., no initial findings of cholestasis) 	Withhold study drug	
 If resolved to Grade 1 or baseline in less than 28 days, resume study drug at the same or a reduced dose at the discretion of the investigator If not resolved to Grade 1 or baseline more than 28 days or worsens or recurs after re-initiating therapy, permanently discontinue study drug If likely immune mediated, seek hepatic consult and consider use of steroids with gradual taper
Grade ≥4 (>20 times ULN or from baseline, if baseline is abnormal)	
Evaluate differential diagnosis and causality (including pre-existing liver disease and infectious etiology) Consider hepatic consult and treat accordingly per standard treatment guidelines If the AST/ALT and bilirubin levels meet the definition of Hy's law, permanently discontinue the study drug
	Permanently discontinue study drug	
 Continue close follow-up until resolution If likely immune mediated, seek hepatic consult and consider use of steroids with gradual taper

ALP = alkaline phosphatase; ALT = alanine aminotransferase; AST = aspartate aminotransferase; COVID-19 = coronavirus 2019; CTCAE = Common Terminology Criteria for Adverse Events; RT-PCR = real-time polymerase chain reaction; TBL = total bilirubin level; ULN = upper limit of normal.

Table 9 Dose Modification/Toxicity Management Recommendations for Infection

Adverse Reaction CTCAE V5.0 Grade/Severity	Recommended Management	Recommended Dosing Modification	Recommended Follow-up

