7.3.5.1 Corrected QT Intervals

The terminology QTc is used in this section as a general notation for QTc using any of the specified methods.

The QT interval data will be corrected for heart rate using 2 correction methods (QTcF and corrected QT interval by Bazett – QTcB). For each QTc correction method, the relationship between QTc and RR at baseline will be evaluated graphically by plotting the logarithm of baseline QTc values against the logarithm of corresponding RR intervals. QTcF will be used as the primary correction method for statistical analysis. If the correlation between QTc and RR intervals remains significant using the Fridericia correction method, an alternative correction method may be considered for statistical analysis in addition to QTcF.

For the statistical analysis based on the primary correction method (QTcF), the mean changes from baseline (Δ QTc) at each time point will be summarized (mean, standard deviation, median and

range, and 2-sided 90% CI). Mean values for the difference and 2 sided 90% CI for mean difference will be calculated at each time point.

The primary analysis will focus on the maximum mean change from baseline in QTc (Δ QTc) on Cycle 1 Day 15, which will be estimated by the mean QTc change at around t_{max} , the time when the C_{max} is reached (i.e., steady state). The same analysis will be performed for Δ QT data using other correction methods if data warrant. The mean change from baseline in QTc (\pm standard deviation) over time will be plotted.

In addition, QTc will be categorized based on International Council for Harmonisation (ICH) E14 guidelines. Tables will present the number and percentage of patients meeting or exceeding the following categories:

- QTc prolongation:
 - Absolute values >450 to ≤ 480 msec
 - Absolute values >480 to ≤ 500 msec
 - Absolute values >500 msec
- QTc change from baseline:
 - Increase from baseline >30 to ≤ 60 msec
 - Increase from baseline >60 msec

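### Two liver-test rows in SAP 17.4 take no account of baseline, so stable elevations admitted at entry are counted as post-baseline incidence

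*SAP*

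**What the plan says.** SAP 17.4 summarizes the incidence of post-baseline liver-test abnormalities in five rows. Two of them matter here: "ALT or AST >3 x ULN and <= 5 x ULN (based on the worst post-baseline case" and "Total bilirubin >= 2 x ULN (based on the worst post-baseline case". The others are ALT/AST above 5 × ULN, ALT/AST above 3 × ULN combined with bilirubin at least 2 × ULN, and Hy's law. SAP 7.4 defines the worst post-baseline value as the highest on treatment, without comparing it with baseline. Apart from these rows, SAP 17.4 provides only listings.

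Protocol 5.1.2, criterion 3, normally excludes AST/ALT above 2.5 × ULN and bilirubin above 1.5 × ULN, but makes two exceptions:

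- "In the dose expansion stage, patients with documented disease infiltration of the liver may have AST and ALT levels" up to 5 × ULN.
- Patients with known Gilbert's disease and normal AST/ALT "who have serum total and direct bilirubin level" up to 2.5 × ULN may enter in either stage.

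Elsewhere the protocol does look at baseline. Section 6.3.1.5 starts its reporting rule with "Treatment-emergent ALT or AST". Table 8 in Section 6.8 grades AST/ALT against ULN "or from baseline, if baseline is abnormal". Section 7.3.2.3 plans a shift of CTCAE grade from baseline to worst on treatment for gradable hematology and chemistry tests.

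**The concern.** A row headed as post-baseline incidence is normally read as what happened after treatment began. Without a baseline condition, a patient who enters inside the range and stays there is counted in the same way as one who moved into it. The bias has only one direction: it can raise these two rates but not lower them.

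Safety is the primary objective in both stages, Protocol 2.4 names hepatic toxicity as a problem of this drug class, and SAP 17.2 makes abnormal hepatic function an event of special interest. There is no control arm to show the background level of abnormality. SAP 8 reports Stage 2 by malignancy type as well as in total, so some denominators are likely to be small.

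**Working it through.** The plan states no figure on this point, so there is none to reproduce. The check has two parts.

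**1. Which rows can be met at entry.** The highest admissible entry value (Protocol 5.1.2) is compared with each SAP 17.4 row. This takes the entry limits as upper bounds on baseline.

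| Entry profile | Max AST/ALT (× ULN) | Max bilirubin (× ULN) | AST/ALT >3 to ≤5 | AST/ALT >5 | Bilirubin ≥2 | Both components (combined, Hy's law) |
|---|---|---|---|---|---|---|
| Ordinary, either stage | 2.5 | 1.5 | no | no | no | no |
| Liver infiltration, Stage 2 only | 5 | 1.5 | **yes** | no | no | no |
| Gilbert's, either stage | normal | 2.5 | no | no | **yes** | no |

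Two of the five rows can therefore contain a patient who has not changed. The two exceptions cannot combine to meet the last two rows: the Gilbert's exception requires normal AST/ALT, and the infiltration exception leaves the bilirubin limit at 1.5 × ULN.

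Examples: a Stage 2 patient with infiltration who enters at ALT 4 × ULN and stays there is counted in the first row. A Gilbert's patient who stays at 2.2 × ULN is counted in the bilirubin row.

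**2. Size.** The documents do not say how many patients entered under the exceptions. One such patient adds 1/n to the rate in a group of n:

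- assumed n = 10, 20, 40: 1/10 = 10, 1/20 = 5 and 1/40 = 2.5 percentage points;
- Stage 2 total of about 100 (Amendment 5 summary): 1/100 = 1 point.

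To show the effect on a whole row, let N be the patients, b those already above threshold who stay there, and t the new-onset rate in the rest. The row as planned counts b + t(N − b). The new-onset count is t(N − b), out of N − b. With N = 100 and assumed b and t:

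| b | t | Row as planned | New onset | Share already present |
|---|---|---|---|---|
| 0 | 5% | 0 + 0.05 × 100 = 5.0 | 5.0 of 100 | 0% |
| 2 | 5% | 2 + 0.05 × 98 = 6.9 | 4.9 of 98 | 2/6.9 = 29% |
| 5 | 5% | 5 + 0.05 × 95 = 9.75 | 4.75 of 95 | 5/9.75 = 51% |
| 10 | 5% | 10 + 0.05 × 90 = 14.5 | 4.5 of 90 | 10/14.5 = 69% |

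At t = 10% the shares for b = 2, 5 and 10 are 2/11.8 = 17%, 5/14.5 = 34% and 10/19 = 53%. These values illustrate the arithmetic and do not estimate what this trial will show.

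**QTc, for comparison.** Protocol 5.1.2, criterion 20, excludes "Congenital long QT syndrome or corrected QT interval (QTc" above 470 msec. Section 7.3.5.1 says "Tables will present the number and percentage of patients meeting or exceeding the following categories", and the lowest absolute category is >450 to ≤480 msec. Entry values above 450 and up to 470 fall inside it: 470 − 450 = 20 of its 480 − 450 = 30 msec. The >480 and >500 categories are out of reach at entry, so one of three absolute rows is affected.

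**The case against.** Several arguments on the other side are sound.

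- *The protocol already plans the remedy.* Its grade shift table would show baseline status test by test, and all results are listed. This stands for the protocol. However, SAP 17.4 does not specify that table, and SAP 7.5 mentions a shift table only as an example. A single-test shift would also not clarify the combined rows.
- *The rows attribute nothing to the drug.* Correct. A reader might infer that pre-existing abnormality is being reported as drug toxicity, but SAP 17.4 only counts post-baseline values. Attribution comes through the adverse-event tables, and Protocol 6.3.1.8 makes a pre-existing condition an event only if it worsens.
- *Hy's law.* A reader might infer that a Gilbert's patient whose ALT rises would be counted as Hy's law on unchanged bilirubin. The text does not establish this. The combined and Hy's law rows are defined by bilirubin and ALT/AST that *increase by* the stated multiples within 14 days, and read literally an unchanged value is not an increase. What remains is an ambiguity: the term could mean reaching the threshold or rising from baseline.
- *QTc.* A reader might infer that the QTc tables ignore baseline. They do not: Section 7.3.5.1 also tabulates increases of >30 to ≤60 and >60 msec, and its primary analysis is mean change from baseline. SAP 17.5 contains no QTc category table.
- *Laboratory abnormalities are a named primary endpoint only in dose escalation*, where the infiltration exception does not apply. This weakens the argument for the ALT/AST row, though safety remains primary in Stage 2.

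**Conclusion.** The point holds for two of the five liver rows. ALT/AST >3 to ≤5 × ULN (Stage 2) and bilirubin ≥2 × ULN (either stage) can include patients who entered in range and did not change. This departs from the protocol's own treatment of abnormal baselines, and the planned shift table that would reveal it is missing from SAP 17.4.

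The size cannot be derived from the documents. It is nil if no one entered under the exceptions; the percentage points above rest on assumed group sizes, apart from the Stage 2 total of about 100. The documents do not support extending the point to all liver thresholds or to QTc as a whole. For the Hy's law row, only the unclear wording is a finding. The change is worth making because the bias is upward, the safety summary is uncontrolled and the cost is small.

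**What to change.** In SAP 17.4:

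1. Keep the fixed ULN thresholds and keep every patient visible, but present each row by baseline status: below threshold, or at or above it. Calculate new-onset incidence among patients below threshold at baseline. For the combined and Hy's law rows, define baseline status by component, since the combination cannot be met at entry.
2. Specify the baseline-to-worst CTCAE grade shift table from Protocol 7.3.2.3.
3. State whether *increase by* in the combined and Hy's law rows means reaching the threshold or rising from baseline.

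Do not apply the multiples to baseline values. Table 8 does so only for AST/ALT grades and keeps fixed ULN limits for Hy's law. Baseline ALT of 4 × ULN would then need to exceed 3 × 4 = 12 × ULN, and Gilbert's bilirubin of 2.2 × ULN would need to reach 2 × 2.2 = 4.4 × ULN, which could hide genuine liver signals.

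Minor: if the QTc categories of Protocol 7.3.5.1 are produced, show the >450 to ≤480 msec row by baseline category. The change-from-baseline categories cover the rest.

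Cost: SAP wording and slightly more programming. Baseline is already defined in SAP 7.2 and the values are collected. The new-onset columns will have different denominators, which should be printed in the table.

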3 OBJECTIVES AND ENDPOINTS

Table 1 Objectives and Corresponding Endpoints

Tier	Objectives	Endpoints
Primary – Dose Escalation	To determine MTD and/or RP2D of HMPL-689 in patients with relapsed, refractory, or resistant lymphoma	
 • Incidence of DLTs • Safety (including but not limited to TEAEs, treatment-related adverse events [TRAEs], SAEs, treatment-related SAEs [TRSAEs], and lab abnormalities)
Primary – Dose Expansion	To further evaluate safety and tolerability of HMPL-689 at MTD in patients with relapsed, refractory, or resistant lymphoma	
 • Safety, including TEAEs and TRAEs
Secondary	To assess preliminary efficacy of HMPL689 in patients with relapsed, refractory, or resistant lymphoma overall and by lymphoma sub-types as assessed by investigator	
 • ORR • TTR • DoR • CBR • PFS
	To characterize PK parameters of HMPL-689 in patients with relapsed, refractory, or resistant lymphoma at both dose escalation and dose expansion stages	
 • Concentration-time profiles and PK parameters after single dose and at steady state
	To evaluate the effect of HMPL-689 on cardiac repolarization, as detected by changes in electrocardiogram (ECG) QTc intervals	
 • QTc interval and HMPL-689 concentration

Abbreviations: CBR = clinical benefit rate; DLT = dose-limiting toxicity; DoR = duration of response; MTD = maximum tolerated dose; ORR = objective response rate; PD = progressive disease; PFS = progression-free survival; PK = pharmacokinetic; RP2D = recommended phase 2 dose; SAE = serious adverse event; TEAE = treatment-emergent adverse event; TRAE = treatment-related adverse event; TRSAE = treatment-related serious adverse event; TTR = time to response.

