6.3.1.4 Abnormal Laboratory Values

Only clinically significant laboratory abnormalities that require active management will be recorded as AEs or SAEs on the CRF (e.g., abnormalities that require IP dose modification, discontinuation of study treatment, more frequent follow-up assessments, further diagnostic investigation, etc).

If the clinically significant laboratory abnormality is a sign of a disease or syndrome (e.g., alkaline phosphatase and bilirubin $5\times$ ULN associated with cholecystitis), only the diagnosis (e.g., cholecystitis) needs to be recorded on the AE/SAE CRF.

If the clinically significant laboratory abnormality is not a sign of a disease or syndrome, the abnormality itself should be recorded as an AE or SAE on the CRF. If the laboratory abnormality can be characterized by a precise clinical term, the clinical term should be recorded as the AE or SAE. For example, an elevated serum potassium level of 7.0 mmol/L should be recorded as “hyperkalemia.”

Observations of the same clinically significant laboratory abnormality from visit to visit should not be repeatedly recorded as AEs or SAEs on the CRF, unless their severity, seriousness, or etiology changes.

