7.3.2.3 Clinical Laboratory Test Values

Descriptive statistics for each clinical laboratory test will be presented for each dose and scheduled visit. Laboratory test values from the hematology and chemistry panels, which are gradable in NCI CTCAE, will be summarized by the shift of NCI CTCAE grade from baseline to the worst grade on study treatment period.

Selected laboratory tests will be plotted over time for each patient. All laboratory test results will be listed.

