7.5. RETESTS, UNSCHEDULED VISITS AND EARLY TERMINATION DATA

In general, for by-visit summaries, data recorded at the nominal visit will be presented. Unscheduled measurements will not be included in by-visit summaries but will contribute to the worst-case value where required (e.g. shift table).

In the case of a retest (same visit number assigned), the latest available measurement for that visit will be used for by-visit summaries.

Listings will include scheduled, unscheduled, retest visits, and early discontinuation data.

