17.6. VITAL SIGNS

The following vital signs measurements will be reported for this study:

- Systolic Blood Pressure (mmHg)
- Diastolic Blood Pressure (mmHg)
- Pulse Rate (bpm)
- Respiratory Rate (breaths/min)
- Temperature (°C)

All vital sign data will be listed.

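### SAP 17.4 and 17.6 specify neither the laboratory CTCAE shift and by-visit summaries nor the vital-sign summary that the protocol requires, although laboratory abnormalities belong to the primary Stage 1 safety endpoint

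*SAP*

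**What the plan says.** **Endpoint.** Protocol section 3, Table 1, defines the primary dose-escalation safety endpoint as "Safety (including but not limited to TEAEs, treatment-related adverse events [TRAEs], SAEs, treatment-related SAEs [TRSAEs], and lab abnormalities"). SAP Table 1 repeats it.

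**Protocol analysis.** Section 7.3.2.3 states: "Descriptive statistics for each clinical laboratory test will be presented for each dose and scheduled visit". It adds that gradable hematology and chemistry values "will be summarized by the shift of NCI CTCAE grade from baseline to the worst grade on study treatment period". The synopsis repeats the shift summary and extends it to normal ranges where a test cannot be graded. Section 7.3.2.4 asks for descriptive statistics on vital signs by dose level and visit.

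**SAP outputs.** Section 17.4 puts all laboratory results into listings and ends: "All laboratory evaluation records and abnormal liver function will be listed". Its one table gives the incidence of ALT/AST and bilirubin elevations above multiples of the upper limit of normal, with combined and Hy's law categories. Section 17.6 names five vital-sign parameters and then says only: "All vital sign data will be listed".

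**SAP conventions.** Section 17 says laboratory results are graded by CTCAE v5.0. Section 7.4 defines the worst post-baseline value as the highest grade on treatment. Section 7.5 says unscheduled measurements "will contribute to the worst-case value where required (e.g. shift table"), and it sets retest rules for by-visit summaries.

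**AE recording.** Protocol 6.3.1.4: "Only clinically significant laboratory abnormalities that require active management will be recorded as AEs or SAEs on the CRF". Its examples are changing or stopping study drug, more frequent follow-up and further diagnostic work-up.

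**The concern.** The SAP says it is based on Protocol Amendment 5, and the current text of that amendment still contains the three summaries. A programmer working from SAP 17.4 and 17.6 would produce listings and a liver table. Measured laboratory toxicity for neutrophils, platelets, hemoglobin, amylase, lipase and the rest of the chemistry panel would then reach a table only through the AE or DLT pages of the CRF.

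That route depends on each investigator's view of what needs active management. A CTCAE grade computed from the laboratory value does not. The difference matters most in Stage 1, where laboratory abnormalities are part of the primary endpoint and dose levels are compared on small numbers. It also matters for this drug: protocol 2.3 reports that the two DLTs seen among 6 patients at 5 mg BID in the earlier Chinese study were asymptomatic Grade 3 amylase increases.

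**Working it through.** No sample size, power or rate is at stake, so the check is a comparison of text.

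**Step 1. Required summaries against specified outputs**

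| Summary | Required by | Specified in SAP section 17? |
|---|---|---|
| Laboratory descriptive statistics by dose and visit | Protocol 7.3.2.3 | No; listing (17.4) |
| CTCAE shift, baseline to worst grade | Protocol 7.3.2.3, synopsis | No; listing (17.4) |
| Vital-sign descriptive statistics by dose and visit | Protocol 7.3.2.4, synopsis | No; listing (17.6) |

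The count is 0 of 3. The liver-threshold table is an addition that the protocol's analysis section does not describe.

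**Step 2. Do the SAP's general sections supply the missing outputs?** Section 7.4 defines worst grade and gives a 7-day window for by-visit summaries. Section 7.5 mentions a shift table as an example, where one is required. Section 7.9 says which statistics describe a continuous variable. Section 8 sets the layout (dose level and total in Stage 1, malignancy and total in Stage 2). These sections say how a table would be built, not that one will be produced for laboratory tests or vital signs. Where the SAP wants a safety table it says so: DLTs in 17.1, TEAEs and AESIs in 17.2, liver thresholds in 17.4. No output in section 17 uses the by-visit rules, and no laboratory output uses the worst-grade rule; the liver table works from multiples of the upper limit of normal.

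**Step 3. What do the other tables capture?**

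- SAP 17.2 tabulates TEAEs by system organ class, preferred term and maximum CTCAE grade, and hepatic AESIs by grade. Laboratory abnormalities entered as AEs are therefore counted by grade.
- SAP 17.1 tabulates DLTs by grade. DLTs are defined as TEAEs in Cycle 1, and the hematologic criteria are narrow: Grade 3 thrombocytopenia counts only with bleeding or platelet transfusion.
- Both routes start from an AE record, so both pass through protocol 6.3.1.4.

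**Step 4. How wide is the 6.3.1.4 filter?** It is not confined to dose changes.

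- *Neutropenia.* Protocol Table 10 recommends a blood count every 2 weeks at Grade 3. From Cycle 3, scheduled hematology falls on Day 1 of each 28-day cycle (5.7.10). A 14-day interval is then more frequent than the scheduled 28 days, and the abnormality would qualify as an AE. In Cycles 1 and 2 (Days 8, 15 and 22, then Days 1 and 15) scheduled counts are already at least that frequent, so this trigger does not operate.
- *Thrombocytopenia.* Table 11 continues the current dose at Grade 3 or lower without bleeding and considers supportive care if it persists. A transient Grade 3 platelet value could therefore appear only in a listing, while a persistent one may be recorded as an AE.

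The filter is real but partial.

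**The case against.** The strongest reply is that this is missing output wording, not a lost analysis. Laboratory grading, worst grade, retest handling, continuous-variable statistics and table layout are all in the SAP, and a shift table is mentioned by name, so the authors probably had these tables in mind. That is plausible, and it is why the point should not be read as a decision to abandon the summaries. It does not close the gap: the outcome sections that drive programming specify listings, and the SAP neither names the tables nor records a departure from protocol 7.3.2.3 and 7.3.2.4.

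A second reply is that graded laboratory toxicity is reported. This stands in part. A reader might infer from 17.4 that it is reported nowhere, or that this component of the primary endpoint has no summary. The documents do not support that: the TEAE, DLT and hepatic AESI tables give grades, and the liver table comes directly from laboratory values. What is missing is any summary of graded values taken from the laboratory data themselves.

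Third, a reader might try to size the shortfall from the 13.6% Grade 3 or higher neutropenia that protocol 2.3 quotes for the Chinese study. That figure is already a TEAE rate, so it cannot stand in for a laboratory rate, and neither document says what fraction of graded values goes unrecorded as AEs.

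Finally, vital signs are not named in the primary endpoint. For them the point is only that protocol and SAP disagree.

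**Conclusion.** The point holds as a gap between protocol and SAP. None of the three summaries required by protocol 7.3.2.3 and 7.3.2.4 is specified in SAP 17.4 or 17.6. Graded laboratory toxicity other than liver thresholds would be tabulated only where it was recorded as an AE or DLT, a subset limited by protocol 6.3.1.4. The primary-endpoint argument applies to the laboratory part, since Table 1 ends its safety list with "treatment-related SAEs [TRSAEs], and lab abnormalities".

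The effect on reported rates cannot be put into numbers from these documents. The conclusion assumes that programming follows the stated outputs of SAP section 17; if table shells outside the SAP already contain the summaries, only the wording needs correcting. It should be fixed before database lock, but it does not threaten the validity of the data.

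**What to change.** In SAP 17.4, add a shift table from baseline to worst on-treatment CTCAE grade for gradable hematology and chemistry tests, using the conventions in 7.4 and 7.5. Present it by dose level and total in Stage 1 and by malignancy type and total in Stage 2. Counts of Grade 3 or higher can be read from this table, so no separate one is needed. For tests that cannot be graded, state whether the normal-range shift in the synopsis will be produced.

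Restore the by-visit descriptive statistics for laboratory tests in 17.4 and for vital signs in 17.6. If the sponsor prefers listings for any of these, record the departure from the protocol in the SAP and justify it.

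The cost is a few sentences of SAP text and standard tables. The data are already collected and the derivation rules are already written.
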